#### **Time to symptom resolution for fever**

Fever (ear temperature  $\geq 38^{\circ}\text{C}$ , base of the tongue temperature  $\geq 37.5^{\circ}\text{C}$ , or axillary temperature  $\geq 37^{\circ}\text{C}$ ) status will be tabulated descriptively by visit. For subgroup of subjects with fever at baseline, time to symptom resolution for fever will be analyzed by using Log-rank test stratified by domain, and step plot of Kaplan-Meier graph will be provided. For subjects without symptom resolution for fever, censoring at (1) the last temperature

measurement time point of the subject, (2) the last temperature measurement time point of all subjects, will both be derived for analysis.

In the protocol (Section 5.2.5.2, Vital signs), it is specified that the body temperature assessed at site on Day 1 should be baseline. Upon review of the data collected on Day 1, it was found that some body temperatures measured by subject before dosing were entered in electronic Patient Reported Outcomes (ePRO). Therefore, the definition of baseline body temperature will be revised to consider the measurement (from either ePRO or on-site) that is closest to the time before dosing on Day 1.

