3.8. Concomitant Therapy

1. The following medication should be prohibited during the specified period:
 - (1) Warfarin is prohibited 14 days prior to screening and the treatment phase.
 - (2) Any other investigational treatment within 30 days before Screening and during study
2. The routine use of antibiotics is not recommended. Antibiotics may be used if bacterial infections are present or suspected. The type of antibiotic will be selected based on the subject's clinical disease status and symptoms with discretion of investigator.

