5.2.2. Demographic data, medical history, and concomitant medication

Demographic data will be collected at the screening visit. Demographic data includes birth year, age, and sex.

Any pre-treatment medical events will be recorded as medical history. The general medical history within 2 weeks before Screening Visit should be recorded at Screening Visit. The general medical history includes chronic diseases, allergic history, surgical history, and disease of interests, such as pulmonary, gastrointestinal, cardiovascular, cerebrovascular, and autoimmune events, cystic fibrosis, dementia, and acute or chronic infection. History of severe renal disease and documented anaphylactic reaction should be recorded in a lifetime basis.

Concomitant medication will be recorded when subjects received the following:

- Medication from 2 weeks prior to screening visit to end of the study
- Any investigational treatment within 30 days prior to the study
- SARS-CoV-2 specific monoclonal antibody or convalescent COVID-19 plasma treatment prior to screening

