5.2.4.6. Electronic Patient Reported Outcome (ePRO)

An ePRO will be used for subjects to record body temperature from Day 1 to Day 7 or beyond to confirm fever-free (as Section **5.2.5.2 Vital signs**) and the IP intake from Day 1 up to Day 6.

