5.2.5.2. Vital signs

The pulse rate, blood pressures in sitting position, respiratory rate, and body temperature will be assessed and recorded in clinic site at each visit. The body temperature assessed at site on Day 1 should be baseline before the start of treatment. Any clinically significant abnormal findings should be record as an adverse event during the study.

After the first dose of CX-4945 or placebo administration on Day 1, subjects will self-measure their body temperature and record it in ePRO four times a day, every 4 to 6 hours.

To confirm fever-free:

After the temperature falls below the fever definition, the subject will continue recording for a minimum of 24 hours.

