## 1 OBJECTIVES AND ENDPOINTS

Objectives	Endpoints
Primary	
To evaluate the effect of intervention with Silmitasertib (CX-4945) in addition to SOC, compared to placebo plus SOC, in preventing the progression of CAP associated with SARS-CoV-2 and influenza virus infection	
 
• The percentage of subjects requiring hospitalization, emergency room visits, or resulting in death due to progression of CAP related to SARS-CoV-2 or influenza. (Time Frame: Day 1 to Day 29)
 

Secondary	
To evaluate the effect of intervention with Silmitasertib (CX-4945) in addition to SOC, compared with placebo plus SOC, in enhancing the subject's clinical condition	
 
• The percentage of subjects with all cause hospitalization, emergency room visits, or death during study period (Time Frame: Day 1 to Day 29)
 
• The percentage of subjects with improved pulmonary X-ray findings for pneumonia, relative to baseline or showing a return to normalcy (Time Frame: Baseline to Day 7, 15, and 29)
 
• Time to symptom resolution for fever The symptom resolution for fever will be defined as body temperature lower than the following definition for 24 hours (ear temperature <math>< 38^{\circ}\text{C}</math>, base of the tongue temperature <math>< 37.5^{\circ}\text{C}</math>, or axillary temperature <math>< 37^{\circ}\text{C}</math>)
 
• Change from baseline in <math>\text{SpO}_2/\text{FiO}_2</math> ratio (Time Frame: Day 1 to Day 7, 15, and 29)
 
• The percentage of subjects exhibiting disease progression in health status Disease progression is defined as an increase of score on the National Institute of Allergy and Infectious Diseases (NIAID) 8-point ordinal scale. (Time Frame: Day 1 to Day 7, 15, and 29)
 
• The percentage of subjects exhibiting health improvement in health status Health improvement is defined as a reduction of score on the NIAID 8-point ordinal scale (Time Frame: Day 1 to Day 7, 15, and 29)
 

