#### **3.4.4 DEFINITION OF BASELINE TEMPERATURE**

The ePRO or on-site temperature measurement may be closer to the actual time of dosing. Therefore, the baseline body temperature will be defined as the measurement from either ePRO or on-site data that is closest to the time before dosing on Day 1.

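### Fever resolution ignores antipyretic use, so drug-masked periods count as resolution; the contrast is probably diluted and can be biased either way, and no planned analysis would show it

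*SAP*

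**What the plan says.** **Definition.** SAP section 1, like Protocol 2.2, states: "The symptom resolution for fever will be defined as body temperature lower than the following definition for 24 hours". The thresholds depend on where temperature is measured.

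**Measurement.** Protocol 5.2.5.2 says that "subjects will self-measure their body temperature and record it in ePRO four times a day, every 4 to 6 hours", and that "After the temperature falls below the fever definition, the subject will continue recording for a minimum of 24 hours". Protocol 5.2.4.6 adds: "An ePRO will be used for subjects to record body temperature from Day 1 to Day 7 or beyond to confirm fever-free". The only other item it assigns to the ePRO is study drug intake.

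**Permitted drugs.** The list in Protocol 3.8 that opens "The following medication should be prohibited during the specified period" names warfarin and other investigational treatment. Baricitinib is barred in Protocol 3.2.3 and 3.4. Antipyretics, NSAIDs and systemic corticosteroids are on no list, and standard of care is whatever each site uses.

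**Recording.** Protocol 5.2.2 requires recording of "Medication from 2 weeks prior to screening visit to end of the study". SAP 3.2.9 summarises this by highest ATC level only. Nothing links it to temperature.

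**Analysis.** SAP 3.2.4 states: "For subgroup of subjects with fever at baseline, time to symptom resolution for fever will be analyzed by using Log-rank test stratified by domain". Both fever analyses in SAP 3.2.11 vary only the censoring time. Under SAP 3.4.4, "the baseline body temperature will be defined as the measurement from either ePRO or on-site data that is closest to the time before dosing"; the dosing meant is the Day 1 dose.

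**The concern.** A temperature can stay below threshold for 24 hours because the fever has ended or because an antipyretic is suppressing it. The endpoint treats these alike. Antipyretics are taken in response to symptoms after randomisation, so randomisation does not guarantee equal use. If CX-4945 shortens fever, placebo subjects may take more antipyretic and be recorded as resolved sooner than they otherwise would be. If use differs between arms for any other reason, a difference can appear with no drug effect behind it.

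Changing the censoring time cannot reveal this, because a masked subject is recorded as an event and is not censored. At stake is the reading of a secondary endpoint, and the only time-to-event endpoint in the plan.

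**Working it through.** **What the plan gives.** There is no power, hazard ratio, event count, fever duration or antipyretic use for this endpoint, so there is no figure of the plan's own to reproduce. SAP 3.4.1 gives 44 randomised; the number febrile at baseline is not stated. Everything below rests on assumed rates. A hazard ratio (HR) above 1 favours CX-4945.

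**Model A, full masking.** True times are exponential with medians of 2 days (CX-4945) and 4 days (placebo), so the true HR is 4/2 = 2.0. A user's recorded time is the smaller of the true time and 1 day. Follow-up is censored at Day 7, with equal arms.

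The log-rank comparison sets observed (O) against expected (E) events. At each event time, E for CX-4945 is total events × the CX-4945 share of those at risk, and HR ≈ (O/E on CX-4945) ÷ (O/E on placebo).

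Worked case, 30% users on CX-4945 and 50% on placebo, per subject in each arm:
- At risk at Day 1: 2^(−1/2) = 0.707 and 2^(−1/4) = 0.841.
- Masked events at Day 1: 0.3 × 0.707 = 0.212 and 0.5 × 0.841 = 0.420. Expected on CX-4945: 0.632 × 0.707/1.548 = 0.289.
- CX-4945 in total (before, at and after Day 1): O = 0.293 + 0.212 + 0.433 = 0.938; E = 0.217 + 0.289 + 0.315 = 0.821.
- Placebo in total: O = 0.159 + 0.420 + 0.272 = 0.851; E = (0.938 + 0.851) − 0.821 = 0.968.
- HR ≈ (0.938/0.821)/(0.851/0.968) = 1.30.

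| True HR | Users, CX-4945 / placebo | HR from O/E | HR from simulated Cox fit |
|---|---|---|---|
| 2.0 | 0 / 0 | 1.97 | 2.00 |
| 2.0 | 30% / 30% | 1.64 | 1.68 |
| 2.0 | 50% / 50% | 1.47 | 1.51 |
| 2.0 | 30% / 50% | 1.30 | 1.22 |
| 2.0 | 40% / 60% | 1.24 | 1.16 |
| 2.0 | 30% / 80% | 0.91 | 0.74 |
| 1.0 (both medians 3 days) | 30% / 30% | 1.00 | 1.00 |
| 1.0 | 30% / 50% | 0.83 | 0.79 |
| 1.0 | 50% / 30% | 1.20 | 1.26 |

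The two columns differ mainly because many events fall together at one day.

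**Model B, partial masking.** The placebo median is 3 days, so λ = ln 2/3 = 0.231 per day. Users have an added false-resolution rate of 0.5 per day. Cox fits used 6,000 simulated subjects per arm, censored at Day 7; with no users they returned 1.49 and 1.93 for true values of 1.5 and 2.0.

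| Users, CX-4945 / placebo | True HR 1.0 | True HR 1.5 | True HR 2.0 |
|---|---|---|---|
| 30% / 30% | 1.00 | 1.39 | 1.72 |
| 50% / 50% | 0.99 | 1.30 | 1.60 |
| 80% / 80% | 1.01 | 1.19 | 1.42 |
| 30% / 50% | 0.84 | 1.13 | 1.41 |
| 50% / 80% | 0.71 | 0.93 | 1.15 |
| 30% / 80% | 0.60 | 0.84 | 0.99 |
| 50% / 30% | 1.18 | 1.55 | 1.91 |

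**When it reverses.** With average false-resolution rates m_t (CX-4945) and m_c (placebo), HR_obs ≈ (λ·HR + m_t)/(λ + m_c). This falls below 1 when m_c − m_t > λ(HR − 1). The required placebo excess is 0.231 × 0.5 = 0.116 per day at HR 1.5 and 0.231 × 1.0 = 0.231 per day at HR 2.0.

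**The case against.** **The current analysis answers a legitimate question.** The trial compares two arms on top of site-defined standard of care, so fever resolution with background care included is a coherent treatment-policy comparison. This stands, and it is why the analysis should stay. The plan does not say that this is the question, and offers nothing to separate it from the end of the fever itself.

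**Full masking by Day 1 is extreme.** Occasional dosing may not keep four daily readings below threshold for 24 hours. This also stands: Model A is an upper illustration. Model B is milder and still shows dilution.

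**A reader might infer that the effect would vanish or reverse at moderate imbalance.** The proportion still febrile after Day 2 in Model A is (1 − user share) × 2^(−2/median). At 30% versus 50% users it is 35% versus 35%; at 40% versus 60% it is 30% versus 28%. But the planned test uses the whole curve. After Day 4 the same model gives 0.7 × 0.25 = 17.5% versus 0.5 × 0.5 = 25%, and 0.6 × 0.25 = 15% versus 0.4 × 0.5 = 20%. Both favour CX-4945, and the hazard ratios stay above 1. No fixed direction is supported.

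**A reader might also infer bias from the baseline rule.** An antipyretic taken before the last pre-dose reading can remove a subject from the febrile subgroup. That reading precedes the first dose in a randomised, double-blind trial, so the subgroup shrinks without systematic bias between arms.

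**A drug-free rule may censor informatively.** A masked subject may stop recording once the minimum 24 hours has passed. This stands in part: the Schedule of Assessments asks for four readings daily from Day 1 to Day 7 or beyond, so many later readings should exist.

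**The stakes are limited.** The endpoint is secondary, in a subgroup of 44 randomised subjects, in a study not sized on power. SAP 3.3.11 lists individual data, and the table and listing specifications are separate documents not available here.

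**Conclusion.** The omission is certain from the text: masked 24-hour periods count as resolution, and no analysis in the SAP would detect them. Its effect is conditional. If CX-4945 works and use is equal or higher on placebo, the contrast is diluted: with full masking, from 2.0 to about 1.7, 1.5 and 1.3 in the three main scenarios. Unequal use can bias the contrast in either direction. With no true effect, 30% versus 50% users gives about 0.83; equal use gives no bias. Reversal needs a large placebo excess (30% versus 80% in Model A at a true 2.0) or a smaller true effect.

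These sizes rest on assumed fever durations, user shares and masking strength; the trial's own distortion cannot be computed from the documents. The consequence is for interpretation of a secondary endpoint, not for a confirmatory conclusion. The plan should be changed, but the trial's main result does not depend on it.

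**What to change.** 1. Keep the current analysis and label it as fever resolution regardless of antipyretic use.
2. Add to SAP 3.2.11 a supportive log-rank analysis, stratified by domain. In it, a 24-hour period counts only if the concomitant medication record shows no antipyretic or NSAID on those calendar days. Use the ePRO readings from Day 1 to Day 7 or later, and date resolution to the first qualifying period. Apply the rule to any NSAID, so that no indication is needed.
3. Subjects with no qualifying period are censored at their own last temperature in one version and at the last temperature time point of all subjects in the other. These are the SAP's existing two rules. Show both, because censoring linked to antipyretic use may be informative.
4. Run a further version that also excludes days on systemic corticosteroids. Keep it separate, since these may be given for other conditions.
5. Tabulate antipyretic, NSAID and corticosteroid use by arm and day in the subset febrile at baseline.
6. Do not attribute a difference, or its absence, to CX-4945 unless the analyses agree.

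**Cost.** A few derived flags, repeated log-rank tests and one table. The last subject left on 22 April 2025 and the SAP is dated 25 June 2025, so no new data can be collected, but the protocol already required medication to be recorded. Day-level dating is conservative and will lose some events in a small subgroup. Patient care does not change.

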**Change from baseline in SpO2/FiO2 ratio**

The SpO2/FiO2 ratio and changes in SpO2/FiO2 ratio will be summarized descriptively by visit. The change from baseline will be analyzed by using ANCOVA.

**The percentage of subjects exhibiting disease progression / health improvement in health status**

NIAID score and changes in NIAID score will be tabulated descriptively by visit. For protocol version 1.0, 6-Point Ordinal Scale collected for subjects of Influenza Virus domain will be converted to corresponding NIAID score (*refer to [Instructions and Abbreviations] of Subject Data Listings Specification for NIAID 6-point Score Conversion to 8-point Score*) and combined with NIAID score for analyses.

The percentage of subjects with increasing NIAID score (exhibiting disease progression) and with decreasing NIAID score (exhibiting health improvement) will be presented with the corresponding Clopper-Pearson exact 95% CI, and tested by using Fisher's exact test or Cochran-Mantel-Haenszel test, respectively.

**The percentage of subjects with a negative RT-PCR result for the SARS-CoV-2 (only for SARS-CoV-2 domain) or the influenza virus (only for influenza virus domain) on Day 7**

The percentage of subjects with RT-PCR negative results will be tested between treatments by using Chi-square test or Fisher's Exact test.

FilmArray data (Negative/Positive) obtained from Protocol v.1.0 will be integrated into and considered equivalent to the results for RT-PCR.

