Return un-used drug				X			X [18]
ePRO [14]		X	X	X	X	X	
SOC/Supportive care				X (as needed)			
Mortality Status		X	X	X	X	X	X
Hospitalization events		X	X	X	X	X	X

Procedure/Assessments	Screening Visit [15]	Treatment Phase			Follow-Up		Unscheduled Visit [17]
		1	2	3	4	5	
Visit	1	2		3	4	5	
Day	Day -2 ~ 1	Day 1 (Baseline)	Day 2 ~ Day 6	Day 7 (EOT)	Day 15	Day 29 (ET/EOS)	
Window Period (Day)				± 1	± 2	± 3	NA
Concomitant Medications	X	X	X	X	X	X	X
Adverse Events		X	X	X	X	X	X

Abbreviations: BID = bis in die, twice a day; ECG = Electrocardiogram; EOT = end of treatment; ET = early termination; EOS = end of study; ePRO = electronic Patient Reported Outcomes; FiO₂ = fraction of inspired oxygen; SpO₂ = saturation of peripheral oxygen; NA = not applicable.

- [1] Informed consent must be obtained prior to patient participation in any protocol-related activities that are not part of routine care. The results obtained from the routine care and associated tests performed within 24 hours before signing informed consent may be collected and utilized as Visit 1 data in this study (Protocol No. CX-4945-011). Additionally, body temperature measurements that fully meet protocol requirements but are taken within 24 hours before signing informed consent can be collected.
- [2] Medical history and current therapies (medications and procedures) will be included up to 2 weeks prior to screening visit. Any pre-treatment medical events will be recorded as medical history.
- [3] A complete physical exam will be performed. Height and weight should be recorded at screening visit (Visit 1) only.
- [4] Vital signs, including blood pressure, pulse rate, respiration rate, and body temperature, will be evaluated at each clinic visit. In addition, subjects will self-report their body temperature by using ePRO [14] from Day 1 to Day 7 or beyond, as needed, with the temperature being measured four times daily at 4 to 6-hour intervals.
- [5] Assessment of health status using the NIAID 8-point ordinal scale will be conducted on Screening, Days 1, 7, 15, and 29.
- [6] Hematology: hemoglobin (Hb), hematocrit (Hct), red blood cells (RBC), white blood cells (WBC), differential of leukocytes, absolute neutrophil count (ANC) and platelets.
- [7] Blood Chemistry:
 - Hepatic function indicators: total bilirubin, alkaline phosphatase (ALP), aspartate aminotransferase (AST), alanine aminotransferase (ALT), total protein, albumin

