 - Renal function indicators: blood urea nitrogen (BUN), serum creatinine, and estimated Glomerular filtration rate (eGFR)
 - Electrolytes: sodium, potassium, chloride, total calcium and bicarbonate
- [8] Coagulation: Prothrombin time (PT) and international normalized ratio (INR)
- [9] ONLY performed on women of childbearing potential. # ONLY performed when early termination occurs before the completion of Visit 3.
- [10] Urinalysis: color, appearance, specific gravity, pH, protein, glucose, occult blood, ketones, leukocyte esterase, nitrite, bilirubin, urobilinogen, and microscopic examination of urine sediment.

Evaluated biomarkers will include: [REDACTED]

[REDACTED]

[REDACTED]

[REDACTED]

- [12] Swabs will be used for rapid diagnostic test, RT-PCR for presence of viral RNA (qualitative tests), Ct value and viral load:
 - At Screening, perform a rapid diagnostic test for SARS-CoV-2 or influenza virus infection using a nasopharyngeal specimen.
 - Nasopharyngeal swab for RT-PCR should be collected on Day 1 and Day 7.

ONLY performed when early termination occurs before the completion of Visit 3.

- [13] Baseline assessments (on Day 1) should be conducted prior to administering the first dose of CX-4945 or placebo. Drug administration is twice daily for 5 consecutive days, starting on Day 1 and completing on Day 5, or on Day 6 if only one dose is administered on Day 1.
- [14] Patients will be instructed on the use of the Electronic Patient Reported Outcomes (ePRO) for all dose administrations and body temperature record [4] at Visit 2. Site staff will check the completeness of ePRO at Visit 3 and Visit 4, and if necessary, at Visit 5. Patients may record dose administration on Day 1 ~ Day 6 and body temperature on Day 1 ~ Day 7 or beyond, as needed.
- [15] Visit 1 and Visit 2 could be the same day. When Visit 1 and Visit 2 occur on the same day, the same assessments from Visit 2 can be omitted.
- [16] The results acquired from Visit 1 should serve as the baseline for the Chest X-ray and 12-lead ECG.
- [17] Adverse events, concomitant medications and hospitalization events will be recorded at an unscheduled visit (UV); other assessments will be performed at the investigator's discretion.
- [18] If the subjects have lost IPs, only one more dispensation of the investigational product is allowed per subject based on the pharmacy manual.

TABLE OF CONTENTS

SIGNATURE PAGE	2
PROTOCOL ACKNOWLEDGEMENT FORM	3
SYNOPSIS	4
SCHEDULE OF ASSESSMENTS	12

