5.2.4. Efficacy Assessments

5.2.4.1. Hospitalization and Emergency Room Visit

If a participant is hospitalized or during emergency room (ER) visit, procedures and assessments will continue per the visit schedule. Hospitalization is defined as inpatient admission and more details are listed in **Section 5.2.5.6.** Hospitalization event will be followed up until Day 29.

This table describes discharge from hospital scenarios if an outpatient is subsequently hospitalized.

Table 5-2 Discharge from hospital (Outpatients Subsequently Hospitalized)

If hospital discharge...	Then....
Occurs prior to Day 29	Subjects will be asked to complete the remaining study assessments at the time points indicated in the visit schedule.
Occurs on the same day as a scheduled study visit	
If the scheduled study assessments are performed during hospitalization and the circumstances meet all the following criteria, assessments do not need to be repeated.
 
• The scheduled study assessments have been performed within 8 hours of discharge.• There has been no change in clinical status.• The information is available to the site.

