5.2.5.6. Hospitalization events

If a subject is admitted to the hospital, the participant will remain in the study and follow the procedures outlined in the visit schedule. Hospitalization is defined as inpatient admission.

The date of hospitalization events will be recorded in the CRF and includes:

- Hospitalization
- Emergency room visit: only for dosed subjects that last 24 hours or longer will be included
- ICU admittance
- Extended care facility (ECF) admittance: ECF events will only be documented for subjects dosed in the trial who experience adverse events (AEs) and require additional medical support in the ECF, such as respiratory therapy to address the AEs. The requirement for additional medical support in the ECF is considered comparable to hospitalization as a discretion by the investigator. This means ECF events occurring before trial enrollment will not be documented. Additionally, enrolled subjects without experiencing AEs move to the ECF after enrollment will not be considered hospitalized and do not need to be entered into the EDC.
- Discharge

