5.2.5.7. Clinical Status and Medications/Procedures of Special Interest

The subject's clinical status and concurrent medications/procedures of special interest will be recorded in the CRF, including the level of consciousness, limitation on activities due to CAP, and requirements for the following:

- Ongoing hospital medical care
- Supplemental oxygen
- Non-invasive ventilation or a high flow oxygen device
- Mechanical ventilation
- ECMO
- Additional organ support (e.g., pressors, renal replacement)

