### **3.2.10 VISIT ADJUSTMENT**

For all efficacy and safety analyses, the visit (not including unscheduled visit) out of acceptable window and the Early Termination Visit (Visit 5) of early terminated subject will be reallocated to an appropriate scheduled visit according to below acceptable visit window.

Visit Name	Visit Day	Acceptable visit window
Visit 1 (Screening)	-1 ~ 1 (v1.0)	NA

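### SAP 3.2.4 has no rule that counts a hospital admission falling wholly between NIAID scoring days as disease progression

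*SAP*

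**What the plan says.** - **Analysis.** SAP 3.2.4 tabulates NIAID scores and changes by visit, then states: "The percentage of subjects with increasing NIAID score (exhibiting disease progression) and with decreasing NIAID score (exhibiting health improvement) will be presented". The percentages get exact confidence intervals and a Fisher or Cochran-Mantel-Haenszel test. Progression is any increase in score and improvement any decrease, with a time frame of Day 1 to Days 7, 15 and 29 (SAP section 1). Neither document has a worst-score, cumulative or event-based rule.
- **Scoring days.** Footnote 5 of the protocol's Schedule of Assessments: "Assessment of health status using the NIAID 8-point ordinal scale will be conducted on Screening, Days 1, 7, 15, and 29".
- **During an admission.** Protocol 5.2.4.1: "If a participant is hospitalized or during emergency room (ER) visit, procedures and assessments will continue per the visit schedule". Admission or discharge triggers no extra score.
- **Unscheduled visits.** Footnote 17 requires adverse events, concomitant medication and hospitalization events; "other assessments will be performed at the investigator's discretion". SAP 3.2.10 covers only scheduled visits: "the visit (not including unscheduled visit) out of acceptable window and the Early Termination Visit (Visit 5) of early terminated subject will be reallocated".
- **The scale.** In protocol Table 5-3, scores 1 and 2 are for non-hospitalized subjects, 3 to 7 for inpatients and 8 for death. There is no level for an emergency room stay.
- **Other recorded data.** Protocol 5.2.5.6: "The date of hospitalization events will be recorded in the CRF and includes" admission, ER stays of at least 24 hours, ICU and discharge. Protocol 5.2.5.7: "The subject's clinical status and concurrent medications/procedures of special interest will be recorded in the CRF", with oxygen, ventilation and ECMO among the items; that section does not mention dates for them.

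**The concern.** The endpoint is named as the percentage of subjects showing disease progression, and it is tested. A reader will take it to include everyone who got worse on the scale. A subject admitted and discharged between two scoring days did get worse on the scale, but the visit-day scores need not show it. If the admission was due to progression of the pneumonia, that subject is a primary-endpoint event, yet can appear in the NIAID table as unchanged or improved.

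If the drug does prevent admissions, more of the unseen progressions would fall in the placebo arm, and the difference in progression would shrink toward zero. That direction depends on the drug having the effect. The information needed to close the gap, the admission date, is already in the CRF.

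**Working it through.** The plan gives no figure on this point, so there is none to reproduce.

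**1. Any admission is an increase.** Entry requires an outpatient, so baseline is 1 or 2 (assuming the subject is still an outpatient on Day 1). An inpatient scores at least 3. The smallest change is 3 − 2 = 1.

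**2. When it is missed.** Suppose a subject is an inpatient on Days 8 to 13 and is scored on Days 7 and 15. The Day 15 result is:

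| Baseline | Day 15 score | Counted as |
|---|---|---|
| 1 | 1 | unchanged (missed) |
| 1 | 2 | progressed (caught) |
| 2 | 2 | unchanged (missed) |
| 2 | 1 | improved (missed) |

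A subject still an inpatient on a scoring day scores 3 or more and is caught.

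**3. Stays that fit between visits.** The gaps are 7 − 1 = 6, 15 − 7 = 8 and 29 − 15 = 14 days. Stays of up to 5, 7 and 13 calendar days can therefore fall wholly inside them.

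**4. Share of stays with no scoring day.** Assume admission on any of Days 2 to 28 with equal weight (27 days) and visits on the nominal days. A stay of L days from admission day a covers a to a + L − 1. It contains scoring day v when v − L + 1 ≤ a ≤ v.

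- L = 2: caught for a = 6–7, 14–15 and 28, which is 5 days. Missed 22/27 = 81%.
- L = 5: caught for a = 3–7, 11–15 and 25–28, which is 5 + 5 + 4 = 14 days. Missed 13/27 = 48%.
- L = 7: caught for a = 2–7, 9–15 and 23–28, which is 6 + 7 + 6 = 19 days. Missed 8/27 = 30%.
- L = 10: caught for a = 2–15 and 20–28, which is 14 + 9 = 23 days. Missed 4/27 = 15%.

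**5. Sensitivity.** If admissions are limited to Days 2 to 14, the shares for 2, 5 and 7 days are 10/13 (77%), 4/13 (31%) and 1/13 (8%). With admissions on Days 2 to 28 and five sets of visit days inside the protocol windows (7/15/29, 6/13/26, 8/17/32, 8/13/26, 6/17/26), the share is 44% to 59% for a 5-day stay and 30% to 37% for a 7-day stay.

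**6. Weight of one subject.** SAP 3.4.1 reports 44 randomized. Taking 44/2 = 22 per arm (assumed from 1:1 allocation), each missed subject moves an arm's progression rate by 1/22 = 4.5 percentage points.

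**The case against.** The strongest reply is that visit-day status is a legitimate quantity and fits the stated time frame. A subject admitted on Day 8 and at score 1 on Day 15 had an event and has also recovered by Day 15. Those statements answer different questions. This stands, and it is why the present analysis should be kept, under a label that says what it is.

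It also stands that the failure is not hidden from the trial. The all-cause hospitalization, ER visit or death endpoint counts these admissions over Day 1 to Day 29, and the primary endpoint counts those due to progression of the pneumonia. A cumulative NIAID measure will largely overlap with the all-cause endpoint.

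A reader might infer from SAP 3.2.10 that unscheduled NIAID scores are discarded. The text does not say so: it governs reallocation of out-of-window and early-termination visits only. Nor does the sentence on the percentages itself repeat that they are by visit, and the table shells are in separate documents (SAP 3.6). What can be said is that the SAP states no rule for using scores or events between visits. The LOCF analysis in SAP 3.2.11 does not supply one, because it fills missing visits.

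**Conclusion.** The gap is real and modest. SAP 3.2.4 has no rule to count an admission between scoring days as progression. The shares (48% for 5-day and 30% for 7-day stays, 81% for 2-day stays) rest on uniform admission over Days 2 to 28, nominal visit days and full return to baseline. Return to baseline is assumed for every subject, so they are upper bounds on the share missed, and they vary strongly with length of stay, which the documents do not give.

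Three stronger readings are tempting and not supported:

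- That most progressions are lost. The highest shares belong to 2-day stays only.
- That the NIAID result is known to be biased, or that any of the 44 subjects was misclassified. The documents show no such case.
- That the trial's conclusions on hospitalization are at risk. The primary and all-cause endpoints are unaffected.

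The trial is exploratory and unpowered, and this concerns two secondary endpoints. It is a cheap improvement to make, and no stated figure is wrong.

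**What to change.** In SAP 3.2.4:

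1. Add a cumulative progression analysis through Days 7, 15 and 29. A subject counts as progressed if any post-baseline NIAID score exceeds baseline, or if the CRF records an inpatient admission or death after baseline and by that day.
2. Use admission and death dates only for this yes/no flag. Do not reconstruct exact scores from oxygen or ventilation records for which the protocol states no dates.
3. Keep the current analysis and label it as visit-day status.
4. Cross-tabulate health improvement at each visit against hospitalization before that visit.
5. State that ER-only stays have no level on the NIAID scale. They are therefore not counted as progression, and they appear in the cross-tabulation.

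**Cost.** A few lines of SAP text, one derived variable and one extra table, from data the protocol already collects.

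**Downsides.** The cumulative measure overlaps with the all-cause endpoint. A subject can be cumulatively progressed and improved on the visit day, which the cross-tabulation will show for hospitalized subjects. ER-only primary events will still not register as progression. If the analysis is added after unblinding, it must be labelled post hoc.
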